5.1.2 Potential risks not associated with pharmacological intervention

Volunteers are potentially exposed to the risks inherent in taking any blood sample such as:

- Pain at the puncture site.
- Extravasation or bruising.
- Peripheral nerve injury (Very rare).
- Infection (Very rare).
- Anxiety.

All these risks will be mitigated by using established and validated protocols in each of the participating institutions, taking timely paraclinical tests, and constant supervision of the study by qualified personnel trained in the study procedures.

5.2 Benefit for volunteers

The study is based on previously reported findings in the scientific literature regarding the potential ability of tenofovir disoproxil/emtricitabine to inhibit SARS-CoV-2 replication (13, 47–50). Therefore, volunteers could benefit from the reduced risk of developing COVID-19 which could mean a decreased risk of developing symptoms, temporary disability, hospitalization, transmission to family members and close contacts, and to other members of the community. Among the possible complications associated with COVID-19, it could reduce the severity or risk of mortality during the follow-up period. Additionally, the continuous and accessible use of EPP for the study volunteers reduces the risk of contagion by COVID-19. The findings of the present study could lead to a change in public policies that in the future will reduce the risk of acquiring COVID-19 by health personnel. In accordance with current Colombian regulations, volunteers will not receive any type of financial compensation for their participation in the study.

6. Report of adverse events

6.1. Definitions

- Adverse event (AE)

Any adverse medical occurrence in a patient or subject of a clinical investigation to whom a pharmaceutical product was administered and that does not necessarily have a causal relationship with this treatment. Therefore, an adverse event (AE) can be any unfavorable and unintended sign (including an abnormal laboratory finding), symptom or illness temporarily associated with the use of a medicinal (research) product, whether it is related. (104).

Considering the above, the United States National Institute of Health in conjunction with the National Cancer Institute of the same country published standardized definitions of adverse events known as Common Terminology Criteria for Adverse Events (CTCAE). Events, for its acronym in English), to describe the severity of the organic damage caused to patients by the various medications (104,105). According to them, the following events are considered:

- Serious adverse event (SAE)

Any unfavorable occurrence than at any dose that:

- Results in death.
- Is life threatening, requires hospitalization of the patient or prolongation of existing hospitalization.
- Results in persistent or significant disability / disability.
- Generates a congenital anomaly / birth defect.

- Fatal Serious Adverse Event.

EAS that end in the death of the subject or threaten the life of the same.

- Expected / Listed Serious Adverse Event.

EAS whose specificity or severity is consistent with that described in the Research Protocol, Investigator's Manual / basic prescription information or product label.

- Unexpected / Unlisted Serious Adverse Event.

EAS whose specificity or severity is not consistent with that described in the Research Protocol, Investigator's Manual / basic prescription information or product label.

- Non-Serious adverse event

All other events that do not meet any of the EAS seriousness criteria

- Adverse event requested

They are the AE that will be searched for in each assessment of the subjects participating in the study.

- Unsolicited adverse events

They are the AEs that are voluntarily manifested by the patient that may or may not be related to the study drug.

6.2. Assessment and documentation of adverse events.

The researcher assigned to follow up the study subjects will be responsible for recording all adverse events in each participating institution, regardless of the group evaluated, with the following exceptions:

A case report form will be created which must have the following information:

- Description of the adverse event
- Date of presentation, duration, and day of resolution.
- Severity according to degrees mentioned
- Conduct taken (need for treatment, suspension of medication, hospitalization)
- The probability of relationship with the drug under study.

All the follow-up of adverse events will be determined according to the Standardized Operational Plan for adverse events of the study.

6.3. Degree of severity

If the definition is met, the degree of severity of adverse events will be categorized. The categorization is found in Table 4 and is based on the (CTCAE) (104,105). According to them and the medicine used, the following events are considered:

Table 4. Adverse event's degree of severity

CTCAE Term	Grade 1	Grade 2	Grade 3	Grade 4	Grade 5
Nervous system disorders					
Headache	Mild pain	Moderate pain; limiting instrumental ADL	Severe pain; limiting self-care ADL	-	-
Insomnia	Mild difficulty falling asleep, staying asleep or waking up early	Moderate difficulty falling asleep, staying asleep or waking up early	Severe difficulty in falling asleep, staying asleep or waking up early	-	-
Gastrointestinal disorders					

Abdominal pain	Mild pain	Moderate pain; limiting instrumental ADL	Severe pain; limiting self-care ADL	-	
Nausea	Loss of appetite without alteration in eating habits	Oral intake decreased without significant weight loss, dehydration, or malnutrition	Inadequate oral caloric or fluid intake; tube feeding, TPN, or hospitalization indicated	-	-
Vomiting	Intervention not indicated	Outpatient IV hydration; medical intervention indicated	Tube feeding, TPN, or hospitalization indicated	Life-threatening consequences	Death
Flatulence	Mild symptoms; intervention not indicated	Moderate; persistent; psychosocial sequelae	-	-	-
Skin and subcutaneous tissue disorders					
Rash maculo-papular	Macules/papules covering <10% BSA with or without symptoms (e.g., pruritus, burning, tightness)	Macules/papules covering 10 - 30% BSA with or without symptoms (e.g., pruritus, burning, tightness); limiting instrumental ADL; rash covering > 30% BSA with or without mild symptoms	Macules/papules covering >30% BSA with moderate or severe symptoms; limiting self-care ADL	-	-
Stevens-Johnson syndrome	-	-	Skin sloughing covering <10% BSA with associated signs (e.g.,	Skin sloughing covering 10 - 30% BSA with	Death

			erythema, purpura, epidermal detachment, and mucous membrane detachment)	associated signs (e.g., erythema, purpura, epidermal detachment, and mucous membrane detachment)	
Allergic reaction	Systemic intervention not indicated	Oral intervention indicated	Bronchospasm : hospitalization indicated for clinical sequelae; intravenous intervention indicated	Life-threatening consequences: urgent intervention indicated	Death

Table 5. Tables for Laboratory Abnormalities

Laboratory abnormality	Mild (Grade 1) **	Moderate (Grade 2)	Severe (Grade 3)	Potentially Life Threatening (Grade 4)	Death (Grade 5)
Laboratory					
ALT and AST	>3 x ULN if baseline was normal. 1.5-3 x ULN of baseline if it was not normal.	>3-5 x ULN if baseline was normal. >3-5 x ULN of baseline if it was not normal.	>5-20 x ULN if baseline was normal. >5-20 x ULN of baseline if it was not normal.	>20 x LSN ULN if baseline was normal. >20 x ULN of baseline if it was not normal.	
Hemoconcentration	Rise of 0-2 g/dl from baseline.	Rise of 2-4 g/dl from baseline.	Rise of > 4 g/dl from baseline.		
Anemia	Hb<ULN-10g/dl	Hb<10-8g/dl	Hb<8g/dl	Life Threatening; Medical	Death

				intervention is required.	
Lymphocytes Decrease - cell/mm³	< 800/mm ³ ; < ULN - 0.8 x 10e9/L	<800 - 500/mm ³ ; <0.8 - 0.5 x 10e9 /L	<500 - 200/mm ³ ; <0.5 - 0.2 x 10e9 /L	<200/mm ³ ; <0.2 x 10e9 /L	
Neutrophils Decrease - cell/mm³	<LLN - 1500/mm ³ ; <LIN - 1.5 x 10e9 /L	<1500 - 1000/mm ³ ; <1.5 - 1.0 x 10e9 /L	<1000 - 500/mm ³ ; <1.0 - 0.5 x 10e9 /L	<500/mm ³ ; <0.5 x 10e9 /L	
Platelets Decreased - cell/mm³	<LLN - 75,000/mm ³ ; <LLN - 75.0 x 10e9 /L	<75,000 - 50,000/mm ³ ; <75.0 - 50.0 x 10e9 /L	<50,000 - 25,000/mm ³ ; <50.0 - 25.0 x 10e9 /L	<25,000/mm ³ ; <25.0 x 10e9	
Creatinine – mg/dL	Rise of 1.5x ULN	Rise of 1.5 – 3x from baseline; 1.5 – 3 x ULN	Rise of 3x ULN from baseline.; 3 – 6 x ULN	Rise of 6x ULN	

ULN: Upper limit of normal range. LLN: Lower limit of the normal range.

Table 5. Causation of adverse events. Taken from the Common Terminology Criteria for Adverse Events (104,105).

Imputed causation	Definition
Definitive	A clinical event, or alterations in laboratory tests, that manifests with a plausible temporal sequence in relation to the administration of the drug, and that cannot be explained by the concurrent disease, or by other drugs or substances. The response to drug withdrawal (withdrawal; dechallenge) must be clinically plausible. The event must be definitive from a pharmacological or phenomenological point of view, with a conclusive re-exposure (rechallenge).
Probable	A clinical event, or alterations in laboratory tests, that manifests with a reasonable time sequence in relation to the administration of the drug, that is unlikely to be attributed to the concurrent disease, or to other drugs or substances, and that when withdrawing the drug presents a clinically reasonable response. Information on re-exposure is not required to assign this definition.

Possible	A clinical event, or alterations in laboratory tests, that manifests with a reasonable time sequence in relation to the administration of the drug, but that can also be explained by the concurrent disease, or by other drugs or substances. Information regarding the withdrawal of the drug may be missing or unclear.
Improbable	A clinical event, or alterations in laboratory tests, that manifests with an unlikely time sequence in relation to the administration of the drug, and that can be more plausibly explained by the concurrent disease, or by other drugs or substances.
Conditional / Not classifiable	A clinical event, or laboratory test abnormalities, reported as an adverse reaction, for which more data is required to make a proper evaluation, or additional data is under review.
Not assessable / Unclassifiable	A notification that suggests an adverse reaction but cannot be judged because the information is insufficient or contradictory, and that cannot be verified or completed in your data.

7. Ethical considerations

This research is considered to have a risk greater than the minimum, since it is a clinical experiment in which a pharmacological intervention will be carried out, according to Resolution 8430 of 1993. Therefore, there may be modifications in the biological variables, and adverse effects from the intervention could occur.

This research will be presented to the Research and Ethics Committee of the Hospital Universitario San Ignacio and the Pontificia Universidad Javeriana, and to the ethics committees of the participating institutions for approval. Attached to this document, the informed consent forms (Annex 4), as well as the corresponding annexes, will be presented. These documents will be thoroughly evaluated and approved when the committee considers that they meet the necessary quality and ethical standards.

To obtain the data, an in-depth explanation of the informed consent will be made to the volunteers in individual sessions. Additionally, the volunteer will be explained the days of clinical follow-up, the possible adverse effects of the intervention, any doubts that may arise will be resolved and it will be made clear to them that they are free to participate or not in the study and that they can be withdrawn at any time. moment.

- Privacy and confidentiality

It will seek to respect privacy, confidentiality and promote the rights and well-being of all the subjects involved in this research defined in article 5 of this same resolution. Additionally, under the support of statutory law 1581 of 2012 "Habeas data", approval will be requested for the handling of personal data in the informed consent. It will be guaranteed that their identification is not taken within the variables to be analyzed in the study, and that, at the time of information analysis, the database is anonymized (each volunteer will have an assignment code that will not be decipherable),

respecting the this way the confidentiality and privacy of the data of each volunteer who is part of the study.

All the data of the study volunteers will be kept in a password-protected database and stored according to the information management protocols for research purposes of the Hospital Universitario San Ignacio and the other participating centers. Volunteers will not be able to access their personal information related to the study.

The database will be known to the principal investigators and will be stored during the study on their computer (s). Researchers will have access for data analysis through a storage platform called "RedCap". This platform complies with the transfer law. Upon completion of the study, a copy of the information will be made, and it will be stored on magnetic media and deleted from the work computer (s). The study information will be stored for up to 5 years after this.

- **Conflicts of interest**

The researchers declare that they have no conflicts of interest. However, if this changes, conflicts of interest will be declared for each researcher. In Annex 7. The conflicts of interest of each of the researchers are presented during the development of the research protocol.

- **Policy of publication and dissemination of results**

No personal information that can identify the study subjects will be disclosed when the research results are published. A report will be prepared with the conclusions of the study to present in the academic-scientific spaces of the San Ignacio University Hospital, the participating centers and in national and international scientific academic events. Additionally, two manuscripts will be prepared for publication in a journal of national or international biomedical interest. The first manuscript about the main results of the study and the second about the description of the kinetics of diagnostic tests in the clinical experiment.

The decision about the order of the authors will be determined by the scientific committee of the experiment, which will be made up of one person from each of the participating institutions.

- **Completion of the study**

The Research and Ethics Committee of the Hospital Universitario San Ignacio and the Pontificia Universidad Javeriana, may decide to terminate the study at any time with prior notice to the researchers and co-investigators.

- **Insurance policy for clinical trials**

This study will have an insurance policy for volunteers in clinical trials that complies with article 13 of Resolution 8430 of 1993 of the Ministry of Health of Colombia. This policy will be taken for a value of COP \$ 70,000,000 MCTE and will cover the probable adverse events caused by the intervention that the volunteers may present.

The policyholder is the Pontificia Universidad Javeriana, and this has been preliminarily contracted with the Previsora, Insurance company. Headquarters Address: [name]. PBX: [contact] / [name].

Table 6. Study schedule

WORK PLAN AND SCHEDULE										
Timetable										
	Preparation and logistics	Recruitment	Follow up				Results	Data analysis	Communication and publication	
Months	1-2	3-5	Visits				5-7	8	8	
Activities			1	2	3	4			Product	Deliverable result
Documentary enlistment of procedures	X								Standard Operating Procedures and Investigator Manual	SOP protocol documents and Investigator Manual
Acquisition of supplies and equipment	X								Diagnostic test kits, PPEs, computers, tablets	Inventories, purchase orders, invoices
CRF design	X								Data extraction form	CRF registration number - Certificate

Training and opening of centers	X								GCP courses carried out in centers, Visits to study centers	Minutes - GCP course approval certificates
Telephone contact potential volunteers		X							Registration with participants interested in being included	Record of execution of the procedure and database in Excel.
Informed consent		X							Signed informed consents	Database of study subjects recruited
Clinical CRF history		X	X	X	X	X			Clinical History of the study subject	Clinical CRF Registry
Clinical Assessment		X	X	X	X	X			Clinical History of the study subject	Clinical CRF Registry
Supervised first dose of drug administration		x							Confirmation of taking at least 1 dose of TDF/FTC or placebo	Drug dispensing registration document
Taking of RT-PCR for SARS-CoV-2		X			X				Positive or negative diagnostic test result	Laboratory report
Antibody IgG - IgM SARS - CoV-2 testing		X		x		x			Positive or negative diagnostic test result	Laboratory report
Sampling for CBC, Creatinine, AST, ALT, P, HIV ELISA, Acs anti HBsAg and		X		X		X			Results of liver, kidney, hematological, electrolyte function tests and pregnancy status in the	Laboratory report

Beta HCG in women									case of participating women.	
Verification of eligibility criteria		X							Determination of the inclusion or not of the participant	Check list
Randomization		X							Random Assignments to Intervention or Placebo	Database
CRF Adverse Events Registry			X	X	X	X			History of adverse events	CRF registration document Adverse event
Finish follow-up and communication to the study subject							X		Formal follow-up completion record	Completion certificate document
Systematization and organization of data							X		Office registry refined with data extracted from the clinical trial	Systematized database
Results analysis								X	Outcome estimates, statistical associations, causality inferences and risks of bias and limitations	Document with results, tables, graphs and data of the study
Communication and publication of results and conclusions.								X	National and international communication of the results and	Two articles of scientific publication, report of results and recommendation

									conclusions of the study	ns of the researchers
--	--	--	--	--	--	--	--	--	-----------------------------	--------------------------

9. Budget

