3.2. Study population

-Reference population: Health care professionals (Physicians, Nurses, Respiratory therapists, or nurse assistants) between the ages of 18 and 70 years, who directly care for confirmed or suspected cases of COVID-19 in the emergency room, general COVID wards or intensive care units.

-Eligible population:

Inclusion criteria

- Medical doctor, Nurse, Respiratory therapist, or nurse assistant who work in the emergency room, general COVID-19 ward, or intensive care unit
- Age: between 18-70 years
- RT-PCR and serology tests for SARS-CoV-2 negative at baseline evaluation

- Direct care of patients in the emergency room, general COVID-19 ward, or intensive care unit
- Informed consent signed

Exclusion criteria

- Two or more of the following
 - ✓ Body temperature higher than 38 Celsius
 - ✓ Cough of recent onset (in the previous 10 days)
 - ✓ Dyspnea
 - ✓ Odynophagia
 - ✓ Malaise, fatigue
 - ✓ Acute diarrheal disease
- History of COVID-19 confirmed by RT-PCR or IgG antibodies
- Family member with suspected or confirmed COVID 19
- cohabitating with a suspected or confirmed case of COVID-19
- Hepatitis B anti-surface antigen antibodies lower than 10mU/ml at baseline evaluation
- Acute or chronic Hepatitis B
- Confirmed diagnosis of HIV infection either by clinical history or ELISA immunoassay at baseline evaluation
- Use of TDF/FTC in the last three months for other clinical conditions
- ALT or AST higher than 2 times the upper reference limit
- Serum hemoglobin <11g/dl or neutropenia<1.000cell/mm³
- Renal dysfunction defined as eGFR lower than 60ml/min (using the CKDEPI formula) or history of Chronic kidney disease
- Known hypersensitivity to TDF/FTC
- Serum phosphorus level <2.5mg/dl
- Use of the following medications (for detailed description see appendix 2):

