- o Hepatobiliary disorders: hepatic steatosis, hepatitis, increased liver enzymes (most commonly AST, ALT)
- o Skin and subcutaneous tissue disorders: rash
- o Musculoskeletal and connective tissue disorders: rhabdomyolysis, osteomalacia (manifested as bone pain and may contribute to fractures), muscle weakness, myopathy.
- o Renal and urinary disorders: acute renal failure, renal failure, acute tubular necrosis, Fanconi syndrome, proximal renal tubulopathy, interstitial nephritis (including acute cases), nephrogenic diabetes insipidus, renal failure, increased creatinine, proteinuria, polyuria.

Most of the adverse events as described are mild and infrequent. Severe events are much rarer and most of them are dose dependent and occur with prolonged use of the drug. During the present study, the intervention time is short, which minimizes the risk of adverse events dependent on the prolonged use of TDF.

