Diastolic blood pressure	Quantitative/discrete	Diastolic blood pressure	Diastolic blood pressure in mmHg
Creatinine	Quantitative/continuous	Serum creatinine concentration (mg/dl).	Serum creatinine concentration (mg/dl).
Creatinine rise	Qualitative/nominal	Severity of creatinine rise	0-Normal 1-Grado 1 2-Grado 2 3-Grado 3 4-Grado 4
IgG for SARS-CoV-2	Qualitative/dichotomous	Result of serology test for SARS-CoV-2 (only for follow-up 2)	0- Negative 1- Positive
Data to be collected in follow-up 3			
Platelets	Quantitative/discrete	Number of platelets in complete blood count (CBC)	Number of platelets per microliter (Cels/ μ l).
Thrombocytopenia	Qualitative/nominal	Severity of thrombocytopenia	0-Normal 1-Grade 1 2-Grade 2 3-Grade 3 4-Grade 4
Hemoglobin (Hb)	Qualitative/continuous	Hemoglobin concentration in CBC	Hb (g/dl).
Anemia	Qualitative/nominal	Classification of severity of anemia	0-Normal 1-Grade 1 2-Grade 2 3-Grade 3 4-Grade 4
Lymphocytes	Quantitative/discrete	Number of lymphocytes in complete blood count (CBC)	Number of lymphocytes per microliter (Cels/ μ l).
Lymphopenia	Qualitative/nominal	Classification of severity of lymphopenia	0-Normal 1-Grade 1 2-Grade 2 3-Grade 3 4-Grade 4
Neutrophils	Quantitative/discrete	Number of neutrophils in complete blood count (CBC)	Number of neutrophils per microliter (Cels/ μ l).
Neutropenia	Qualitative/nominal	Classification of severity of neutropenia	0-Normal 1-Grade 1 2-Grade 2 3-Grade 3 4-Grade 4
Aspartate aminotransferase (AST)	Quantitative/continuous	AST concentration in international units per liter (UI/l)	AST (UI/l).
Aspartate aminotransferase elevation	Qualitative/nominal	Severity of elevation of AST	0-Normal 1-Grade 1 2-Grade 2 3-Grade 3 4-Grade 4
Alanine aminotransferase (ALT)	Quantitative/continuous	ALT concentration in international units per liter (UI/l)	ALT (UI/l).
Alanine aminotransferase elevation	Qualitative/nominal	Severity of elevation of ALT	0-Normal 1-Grade 1 2-Grade 2 3-Grade 3 4-Grade 4

Pregnancy test	Qualitative/dichotomous	Applicable only to women. Result of quantitative serum Beta-HCG test regarding upper reference value for non-pregnant women.	0- Negative 1- Positive
RT-PCR SARS-CoV-2	Qualitative/dichotomous	Detection of SARS-CoV-2 by RT-PCR de	0- Undetectable 1- Detectable
Data to be collected only in Follow-up 4			
Follow-up date	Quantitative/continuous	Follow-up date	Day/month/year

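### With a normal baseline, ALT/AST Grade 1 in Table 5 starts where Grade 2 starts, so rises up to 3 x ULN have no grade and higher values meet two grades

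*Combined protocol and SAP*

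**What the plan says.** The laboratory version of Table 5 (section 6.3; a second table with the same number deals with causation) grades ALT and AST in one row with two limbs, according to whether the baseline was normal.

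- Grade 1: ">3 x ULN if baseline was normal. 1.5-3 x ULN of baseline if it was not normal".
- Grade 2: ">3-5 x ULN if baseline was normal. >3-5 x ULN of baseline if it was not normal".
- Grade 3: ">5-20 x ULN if baseline was normal. >5-20 x ULN of baseline if it was not normal".
- Grade 4: above 20 x, on the same two limbs.

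Other parts of the protocol depend on this row or bear on it:

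- Section 3.2 excludes anyone with "ALT or AST higher than 2 times the upper reference limit". Appendix 3 records this criterion as liver dysfunction.
- Section 6.2 requires the adverse event form to carry a severity grade.
- Appendix 3, follow-up 3, holds a field defined as "Severity of elevation of ALT", with a matching field for AST. The only codes are 0 (normal) and Grades 1 to 4. The measured concentrations are stored separately as continuous variables.
- Section 5.1.1 lists among post-marketing reactions to tenofovir "hepatic steatosis, hepatitis, increased liver enzymes (most commonly AST, ALT").

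**The concern.** A grading scale should give each abnormal value exactly one grade. With a normal baseline this row does not. It assigns nothing to the range just above normal, where mild elevations lie, and it assigns two grades to everything above 3 x ULN. Safety is a stated objective, raised transaminases are a reaction the protocol itself lists, and section 4.1 explains that there is no data monitoring committee. The coding rule used at each centre therefore has to be unambiguous.

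Two further features make the row hard to apply. A value that would have barred someone from entering the trial can arise on treatment and have no grade. For abnormal baselines, the text expresses the threshold as a multiple of both ULN and baseline, and these give different answers for the same participant.

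**Working it through.** There is no planned figure to reproduce, so the check applies the row literally.

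**Normal baseline.** Inputs are the four normal-baseline limbs of the ALT/AST row. Grade 1 is above 3; Grade 2 is above 3 to 5; Grade 3 is above 5 to 20; Grade 4 is above 20 (all x ULN).

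| Value on treatment (x ULN) | Grades satisfied |
|---|---|
| above 1, up to 3 | none |
| above 3, up to 5 | 1 and 2 |
| above 5, up to 20 | 1 and 3 |
| above 20 | 1 and 4 |

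The ungraded band includes everything above 2 and up to 3 x ULN, which section 3.2 treats as grounds for exclusion. A participant who goes from normal to 2.5 x ULN is above the entry limit but has no grade.

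**Abnormal baseline.** Entry allows baselines up to 2 x ULN. Take a baseline of 1.9 x ULN and read the Grade 1 limb (1.5 to 3) both ways.

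- As multiples of the participant's own baseline, Grade 1 starts at 1.5 x 1.9 = 2.85 x ULN and Grade 2 starts above 3 x 1.9 = 5.7 x ULN.
- As multiples of ULN, Grade 1 starts at 1.5 x ULN, which is already met with no change from baseline, and Grade 2 starts above 3 x ULN.

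A value of 4 x ULN in this participant is 4 / 1.9 = 2.1 x baseline, so it is Grade 1 on the first reading and Grade 2 on the second. On either reading the bands are contiguous and do not overlap; the fault in this limb is only the undefined reference.

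**Across the two limbs.** Two participants both reach 2.9 x ULN. The one who started normal has no grade. The one who started at 1.9 x ULN has reached 2.9 / 1.9 = 1.53 x baseline and is Grade 1 on both readings. The larger relative rise has no grade and the smaller one does.

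**Comparison within the table.** Neutrophil Grade 1 runs from the lower normal limit to 1500/mm³, where Grade 2 begins. Platelet Grade 1 runs from the lower normal limit to 75,000/mm³, where Grade 2 begins. In both rows Grade 1 starts at the limit of normal and stops where Grade 2 starts. The normal-baseline limb for ALT and AST does neither.

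**Where the data are affected.** An ALT of 2.5 x ULN after a normal baseline has no valid entry in the Appendix 3 severity field: code 0 would be false and a blank would be a missing value. The severity item on the adverse event form has the same problem. The non-serious event list in Appendix 3 has no liver-enzyme code apart from the free-text option, so the AST and ALT severity fields are the dedicated place for this information. Table 1 and Appendix 3 both place post-baseline AST and ALT at day 60, so under them no later scheduled value would supply the missing grade.

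**The case against.** A reader might infer that mild liver toxicity disappears from the safety data, or that a real excess on the drug would be reported as no liver events. The documents do not support that.

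- Section 6.1 counts an abnormal laboratory finding as a possible adverse event and sets no minimum grade.
- Section 6.3 puts grading after that decision: "If the definition is met, the degree of severity of adverse events will be categorized". A missing grade does not cancel the event.
- Section 3.6.8 has results read against each laboratory's normal values as well as the protocol's grading criteria.
- The raw AST and ALT concentrations are kept, so elevations can be tabulated or regraded by arm later.
- Section 4 analyses total and serious adverse events, not events by grade.
- The withdrawal criteria in section 3.6.9 name a kidney grade but no liver grade.

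All of this stands, and it limits the point to severity coding. It is also fair to say that no passage tells sites to code such values as normal; they might leave the field blank instead.

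A second objection is that this is a typing or translation slip. That is plausible: the Grade 1 column header carries an asterisk mark with no visible note, and the Grade 4 cell contains a stray abbreviation. The intended rule is therefore uncertain. The Grade 1 cell itself is complete and legible, however, and sites following it as written would meet the gap and the overlap.

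**Conclusion.** The defect is real and modest. With a normal baseline, values above 1 and up to 3 x ULN have no grade, and values above 3 x ULN satisfy Grade 1 and one higher grade at once. With an abnormal baseline the reference point is not settled. The consequences are that mild elevations are coded normal or left blank in the two severity fields and lack a grade on the adverse event form, that graded liver tables would undercount them in both arms, and that sites could differ on values above 3 x ULN. The total and serious adverse event analyses do not use the grade.

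The number of participants affected cannot be derived from the documents. They give no distribution of ALT or AST in healthy staff, and the only liver-enzyme frequencies in section 5.1.1 come from a 144-week HIV treatment trial in which the drug was given with efavirenz. The conclusion depends only on the literal bands, not on any assumed drug effect on the liver.

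**What to change.** The sponsor should reconcile the Grade 1 and Grade 2 cells for normal baselines so that the bands are contiguous, do not overlap, and cover values above the normal limit, following the pattern of the neutrophil and platelet rows. For abnormal baselines, it should state a single reference, either ULN or the participant's own baseline, in all four grades. The reconciled row should then govern the AST and ALT severity fields in Appendix 3 and the severity entry on the adverse event form. The thresholds are for the sponsor to settle, because section 3.6.8 ties these criteria to the physician's decision on whether a participant continues.

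The cost is a correction to one table row and the matching form guidance. AST and ALT are already sampled, so no extra testing is needed. The small downside is that more mild laboratory abnormalities will be graded in both arms.
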